4.3 Subject Recruitment and Screening

Recruitment and Informed Consent

Nonimmune, nonviremic liver transplant patients on SRL therapy meeting I/E criteria (except for liver biopsy which will be performed only if all other I/E criteria met) will be approached consideration and informed consent into the study. The consent form will include discussion of the risks/benefits of their current therapy (SRL) and the planned minimization/withdrawal. Specifically, the risks of minimization/withdrawal (i.e. developing acute or chronic rejection, alloimmune hepatitis during any portion of the study) and procedural risks will be a major emphasis of the consent process. The consent form will also include the strict requirement for patients to follow all instructions from the PI in regard to the close laboratory follow-up occurring throughout the trial, to diagnose any episode of rejection or concern (elevation of liver transaminases) as early as possible to be able to respond appropriately. All of the study procedures will be discussed with the patient during clinic visits. They will be informed that neither participation nor refusal will influence their clinical care. All laboratory tests or costs related to their care in the study, with the exception of non-standard of care items (i.e. liver biopsy, IM assays), will be the responsibility of the patient and/or his/her insurance company. They will be asked a few questions afterwards to verify comprehension and then sign the consent form documenting their agreement to participate. A signed copy of the consent form will be given to them. Participation is completely voluntary and they may discontinue participation in either study at any time without affecting their care.

Screening Evaluation at the time of Minimization/Withdrawal

If the patient agrees and signs consent, history and physical, QOL (quality of life) survey, and screening laboratories (CBC, CMP, Trough IS level, HbA1C, Lipid profile, Urine prot/cr ratio) will be performed. Following this, single pass liver biopsy (histology and graft immunohistochemical [IHC] assays) and blood assays will be performed as part of the immunological monitoring protocol. In addition, the liver biopsy will be used to determine stability in graft function (i.e. no evidence of rejection or immune-mediated hepatitis) before considering minimization. SRL minimization/withdrawal will only be performed if clinically, biochemically and histologically (by biopsy) stable, following the I/E criteria. Patients entering the minimization/withdrawal phases will be reduced every month by 50% of total dose until they reach 0.5 mg daily for one month. They will then be reduced further by to 0.5 mg every other day, then twice weekly, then once weekly (all separated by one month at a time) dosing. This should take approximately 6 months to complete the minimization phase as most patients are currently on 1-3 mg of SRL daily. Throughout the study time period, liver function tests will be monitored every 2 weeks. For

any patient throughout the study developing liver dysfunction (direct bilirubin >1 mg/dL; ALT, AST, or AlkPhos > 2xULN), this will be confirmed on a repeat blood test within 1-2 weeks and if persistent, liver biopsy will be performed. Immediately before complete withdrawal, i.e. repeat clinical (screening labs) and blood assays will be performed. If complete withdrawal is deemed safe (no evidence of biochemical abnormalities, i.e. direct bilirubin < 1 mg/dL; ALT, AST, or AlkPhos < 2xULN), patients will be withdrawn completely (i.e. the once/week SRL dose discontinued) and followed off SRL therapy for one year. In this time period, liver function tests will be monitored every 2 weeks. At 12 months following withdrawal, the same history and physical, QOL survey, screening labs and blood IM assays will be performed as in the study initiation, as well as the liver biopsy- all for the primary endpoint. If rejection or immune-mediated hepatitis is seen on this post-withdrawal biopsy or at any time during the study period, the patient will be reinitiated on IS therapy appropriately per the PI and not have another withdrawal attempt. All patients will be followed until 1 year post-attempted withdrawal, even if unsuccessful, although patients developing rejection or resumption of IS prior to this period will not have a final liver biopsy performed (i.e. only those presumed tolerant or who did not have rejection).

Blood and Tissue Samples

Standard of care laboratories complete blood count, liver function tests (CBC, LFTs) will be performed every 2 weeks on all patients. Please see Figure 1 above for sample collections. A separate clinical informed consent will be obtained each time a liver biopsy is performed. If the patient develops elevation in liver transaminases requiring a liver biopsy at any stage of the minimization/withdrawal phase, blood assays will be requested from the patient at the time of the biopsy. These immunological data in rejecting patients will be important to compare to patients who successfully are minimized and withdrawn.

Follow-up

Laboratory follow-up (CBC, CMP) is described above- every 2 weeks throughout the trial. Any biochemical (or clinical) signs or significant liver function test abnormalities will be acted on immediately either by liver biopsy or resumption of the recent IS dose. All patients will be seen in the clinic every 3 months to assess for any new signs or symptoms or resolution of drug side effects in the minimization or withdrawal arm. The Post Liver Transplantation Quality of Life and Promis-29 quality of life surveys and IS cost tally will be performed prior to the study onset and after successful vs. unsuccessful withdrawal (end of study).

4.4 Early Withdrawal of Subjects

4.4.1 When and How to Withdraw Subjects

Subjects may be withdrawn from the trial at any time for any reason, either by personal choice or due to medical indications. Subjects who are non-compliant with study guidelines, medications and clinic examinations will be withdrawn from the study. The NU IRB may also discontinue the study at any point. The subjects will be fully informed of these actions.

4.4.2 Data Collection and Follow-up for Withdrawn Subjects

If patients are withdrawn prematurely, they will still be followed through the follow-up time period of the study and beyond as per standard medical care. These data are important to collect to determine differences in this group compared to those who completed the study. This will include patient and graft survival data, as well as laboratory values and immunosuppressive therapy. If the subject is lost to follow-up, we will make every attempt to contact the patient (i.e. phone calls, certified letters, attempts at contacting next-of-kin, etc).

5 Subject Compliance Monitoring

5.1 *Subject Compliance Monitoring*

The investigator and research coordinator will have full contact with the patient throughout the course of the study. Subjects will be seen in the clinic at baseline and every three months through the study. Laboratory tests will be monitored by the investigator and research coordinator, and lapses in compliance with laboratory tests will be determined by monitoring a schedule of events and follow-up for each patient. In addition, the patient will be called on a monthly basis prior to each tapering of SRL therapy to document compliance with the dosing and for any new symptoms. Persistent non-compliance will be an indication to remove the patient from the study, per investigator discretion.

5.2 *Prior and Concomitant Therapy*

All concomitant medicines will be collected at each study visit (ie; every 3 months). There are no restrictions on concomitant medicines/therapies except for additional immunosuppression (IS) therapy or other therapies deemed unsafe per the investigator.

6 Study Procedures

- 6.1 **Visit 1: Screening/Pre-Withdrawal:** (occurs at a Standard of Care Visit): If the patient agrees after reading through the consent and discussing the study with the study physician and/or research coordinator/nurse they sign the consent, then a history and physical will be performed. The Post Liver Transplantation Quality of Life and Promis-29 quality of life surveys will be administered and, laboratory tests (CBC, CMP, Trough SRL level, HBa1C, Lipid profile, Urine prot/cr ratio, and tolerance/immunophenotyping/genomic/proteomic assays) will be performed.
- 6.2 **Visit 2: Liver Biopsy (+2 weeks of Screening/Pre-Withdrawal Visit):** Single pass liver biopsy (histology and graft immunohistochemistry assays) and blood immune/biomarker (tolerance/immunophenotyping/genomic/proteomic) assays will be performed as part of the immunological monitoring protocol.
- 6.3 **Monitoring during Minimization (No visits):** SRL minimization will only be performed if clinically, biochemically and histologically (by biopsy) stable, following the I/E criteria. Patients entering the minimization phases will be reduced every month by 50% of total dose until they reach 0.5 mg daily for one month. They will then be reduced further by to 0.5 mg every other day, then twice weekly, then once weekly (all separated by one month at a time) dosing. This should take approximately 6 months to complete the minimization phase as most patients are currently on 1-3 mg of SRL daily. Throughout the study time period, liver function tests will be monitored every 2 weeks. For any patient throughout the study developing liver dysfunction (direct bilirubin >1 mg/dL; ALT, AST, or AlkPhos > 2xULN), this will be confirmed on a repeat blood test within 1-2 weeks and if persistent, liver biopsy will be performed.
- 6.4 **Visit 3: End of Minimization and Pre-Withdrawal (6 month clinic visit):** Immediately before complete withdrawal, i.e. repeat clinical (screening labs as SOC, except SRL level not needed) and blood (tolerance/immunophenotyping/genomic/proteomic- research) assays will be performed. If

complete withdrawal is deemed safe (no evidence of biochemical abnormalities, i.e. direct bilirubin < 1 mg/dL; ALT, AST, or AlkPhos < 2xULN), patients will be withdrawn completely (i.e. the once/week SRL dose discontinued) and followed off SRL therapy for one year. In this time period, liver function tests will be monitored every 2 weeks as per 6.3 above. A history and physical will be performed as SOC (every six months visits are SOC at our transplant center).

6.5 **Visit 4: Post-Withdrawal (12 month clinic visit- SOC):** history and physical, laboratories (CBC, CMP) will be performed. In this time period, liver function tests will be monitored every 2 weeks as per 6.3 above.

6.6 **Visit 5: Post-Withdrawal (18 month clinic visit- study end):** At 12 months following withdrawal, the same history and physical, the Post Liver Transplantation Quality of Life and Promis-29 quality of life surveys, labs (CBC, CMP, HBs1C, Lipid profile, Urine prot/cr ratio- SOC; and tolerance/immunophenotyping/genomic/proteomic assays- research) will be performed as in the study initiation, as well as the research liver biopsy- all for the primary endpoint. If rejection or immune-mediated hepatitis is seen on this post-withdrawal biopsy or at any time during the study period, the patient will be reinitiated on IS therapy appropriately per the PI and not have another withdrawal attempt. All patients will be followed until 1 year post-attempted withdrawal, even if unsuccessful, although patients developing rejection or resumption of IS prior to this period will not have a final liver biopsy performed (i.e. only those presumed tolerant or who did not have rejection).

7 Statistical Plan

7.1 Sample Size Determination

We do not plan to utilize a control/non-withdrawn or CNI comparator group as 1) this is an initial pilot mechanistic study; 2) patients can serve as their own control (rejection vs. success) for this initial effort; 3) our prior studies have shown that statistically significant changes in the blood/graft biomarkers can be detected with just 20 patients. These results will be critical in guiding power calculations for larger, prospective, controlled studies testing the specific biomarker predictors that are identified herein and whether SRL vs. CNI withdrawal is associated with a higher % of tolerance. In addition, our sample size is limited by our available funds and the numbers of patients on SRL monotherapy in our center (estimated around 40)

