1.2 Preclinical Data

Preliminary Data: We demonstrated that liver transplant (LT) recipients on SRL monotherapy had higher percentages of peripheral blood mononuclear cell (PBMC) immunophenotypic Tregs (CD4+CD25Hi+Foxp3+ cells) compared to recipients on CNIs (12). This led to a recently published CNI to SRL conversion trial demonstrating increased percentages of PBMC/bone marrow Tregs and PBMC DCregs (ILT3/4+) in LT recipients converted from tacrolimus to SRL monotherapy (13). Liver biopsy immunohistochemistry FOXP3:CD3 and CD4:CD8 ratios were significantly higher after conversion. Patient sera on TAC but not SRL suppressed Treg generation in mixed lymphocyte reactions. Finally, consistent with prior reports of genomic expression patterns and cellular assays as signatures of tolerance (16), we detected the expression of 289 novel genes and 22 proteins, several important in immunoregulatory pathways, after SRL conversion. In a separate in vitro study, we also demonstrated robust allospecific regulatory effects of SRL in Treg mixed lymphocyte reactions (14). Our preliminary data, in conjunction with other clinical and laboratory reports, provide the mechanistic rationale for the

concept that SRL may facilitate IS withdrawal in LT and that such assays should be tested in parallel as biomarkers of tolerance. We hypothesize that SRL will promote regulatory gene/protein expression patterns in the peripheral blood AND in the allograft, which can then be utilized as predictive assays in tolerance trials. To robustly test this hypothesis, we will collect serial blood and allograft samples before/after withdrawal and at the time of biopsy for possible rejection, all to be tested as markers of immunoregulation. This will consist of assays similar to those performed in our recent work (12, 13, 21).

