Standard of care laboratories (CBC, CMP) will be performed every month on all patients, and only LFTs performed in the interim 2 weeks between each month (non-standard of care; covered by the study funds) until complete withdrawal. 3 green top 5 mL and 3 red top 5 mL tubes of blood for biomarker assays will be taken on all patients prior to study enrollment, prior to complete withdrawal, and one year after withdrawal or at the time of suspected rejection. Liver biopsy (one 3 cm biopsy- 2 cm for histology and 1 cm for genomic assays) will be performed at baseline (pre-minimization) and 1 year post withdrawal. A separate clinical informed consent will be obtained each time a liver biopsy is performed. If the patient develops elevation in liver transaminases requiring a liver biopsy at any stage of the study protocol, blood (all for immune monitoring (IM) assays) will be requested from the patient at the time of the biopsy. If rejection occurs, the patient will be followed in the study until completion but not be further withdrawn from SRL or have a liver biopsy at the end of the study

Follow-up

Laboratory follow-up is described above- every 2 weeks throughout the trial until complete withdrawal. Any biochemical (or clinical) signs or significant liver function test abnormalities will be acted on immediately either by liver biopsy or a pause in IS withdrawal per investigator discretion. All patients will be seen in the clinic every 3 months to assess for any new signs or symptoms or resolution of drug side effects in the minimization or withdrawal arm. Quality of life questionnaires; Post Liver Transplant

Quality of Life Instrument (pLTQ) and the Promis-29 profile v1.0 will be administered at the study onset and after successful vs. unsuccessful withdrawal (end of study)

Outcome Measures

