The primary outcome will be the proportion of patients off SRL therapy with normal liver biochemistry and graft histology at 12 months (i.e. tolerant). Thus, the incidence of graft dysfunction (acute rejection, immune mediated or autoimmune hepatitis, chronic rejection) or non-tolerance will be assessed in this SRL withdrawal group and compared to the historical CNI group (20% tolerant; 80% failure) as the primary endpoint. This rate will be a composite of the cumulative number of biopsy-proven graft dysfunctions requiring conversion back to SRL or additional IS therapy or discontinuation of minimization/withdrawal that occur during the course of the study. Major secondary measures compared will be the predictive capacity of the blood and graft biomarker assays (immunophenotyping, genomic/proteomics) before and after minimization/withdrawal in the success vs. failure groups. Clinical secondary outcomes will be compared: the number of infectious complications, liver biopsy complications, cardiovascular outcomes (i.e. blood pressure, diabetes control, lipid levels), renal function, hematopoietic parameters, gastrointestinal effects, or other side effects of SRL that may or may not improve or develop with minimization/withdrawal. These will all be documented by a study database during patient visits, electronic charts and/or by phone communication. Finally, quality of life (Post Liver Transplant Quality of Life Instrument (pLTQ) and the Promis-29 profile v1.0) will be analyzed at the end of the study to determine the effect of IS minimization/withdrawal on other health benefits.

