7.2 Statistical Methods

We have performed within subject comparisons and measurements on PBMC and biopsy using appropriate paired analysis (paired t-test or equivalent nonparametric test (Wilcoxon Signed Rank test) (12, 13). Repeated measures of analysis of variance (RM-ANOVA) were used to test the trajectory variations over time. Two-sided F-test statistics were applied using $\alpha=0.05$. For proteogenomic bioinformatics analysis, we have reported for each gene/protein comparison the T-test p-value, its non-parametric analog (Kruskal Wallis test), the fold change, and for multi-analyte signatures, the AUROC curve (C-index) and the q-values by member genes/proteins. We were then able to calculate the predictive accuracy, sensitivity and specificity of each signature. For clinical endpoints, categorical and continuous variables will be analyzed with appropriate tests (Fisher's exact, T-test). $P<0.05$ will be considered significant

7.3 *Subject Population(s) for Analysis*

All subjects (successful vs. failed, withdrawn from the study vs. maintained) will be followed and analyzed at study end. We will also document the number of patients screened who did not meet I/E criteria at the study initiation.

8 Safety and Adverse Events

8.1 *Definitions*

Adverse Event

By definition an **adverse event** (AE) is defined as: any symptom, sign, illness or experience that develops or worsens in severity during the course of the study. Intercurrent illnesses or injuries should be regarded as adverse events. Abnormal results of diagnostic procedures are considered to be adverse events if the abnormality:

- results in study withdrawal
- is associated with a serious adverse event
- is associated with clinical signs or symptoms
- leads to additional treatment or to further diagnostic tests
- is considered by the investigator to be of clinical significance

Adverse events are classified as serious or non-serious.

Serious Adverse Event

. A **serious adverse event** is any AE that is:

- fatal
- life-threatening
- requires or prolongs hospital stay
- results in persistent or significant disability or incapacity
- a congenital anomaly or birth defect
- an important medical event

Events that are expected, anticipated, related to the standard of care treatment or known adverse events/serious adverse events from standard of care medications or pre-existing conditions will not be reported.

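### Success versus failure is a between-patient comparison, not an own-control one; at 20 to 25 patients a missed biomarker correlation is inconclusive, and no internal validation of signatures is specified

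*Combined protocol and SAP*

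**What the plan says.** Section 7.1 gives three reasons for having no control or CNI comparator group. The second is that "patients can serve as their own control (rejection vs. success) for this initial effort". The third is that "our prior studies have shown that statistically significant changes in the blood/graft biomarkers can be detected with just 20 patients". It then says: "These results will be critical in guiding power calculations for larger, prospective, controlled studies testing the specific biomarker predictors that are identified herein".

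Under Outcome Measures, section 3.1 makes the predictive capacity of the biomarkers a major secondary measure, compared "before and after minimization/withdrawal in the success vs. failure groups". Under Blood and Tissue Samples, it schedules blood for the assays "prior to study enrollment, prior to complete withdrawal, and one year after withdrawal or at the time of suspected rejection". The Study Overview in 3.1, section 4.3 and section 6.6 all rule out a second withdrawal attempt after rejection.

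The Study Overview also names two outcomes, joined by 'or', that would make large trials unnecessary: no demonstrated correlation between biomarkers and withdrawal outcome, or a low tolerance rate (under 20% is its example).

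Section 7.2 describes the biomarker methods mostly in the past tense: "We have performed within subject comparisons and measurements on PBMC and biopsy using appropriate paired analysis". For multi-analyte signatures it lists "the AUROC curve (C-index) and the q-values by member genes/proteins", and then says that accuracy, sensitivity and specificity were calculated. It mentions no cross-validation, bootstrap or hold-out sample.

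**The concern.** A patient either succeeds or fails, so nobody supplies both sides of a success versus failure contrast. If the own-control wording and the 20-patient statement are taken as support for that contrast, the sample looks more adequate for the predictive aim than it is.

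Two uses of the biomarker result are at stake. A null result could be read under 3.1 as a reason not to run a larger trial, when a sample this small cannot tell a true absence from a miss. A positive result feeds the power calculations for later studies. If signature accuracy is scored on the same patients used to choose the markers, those calculations would start from optimistic figures.

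**Working it through.** **The plan's own figure.** Section 3.1 points to sample size calculations in the statistical section, but 7.1 gives no power, effect size or SD. The ceiling of 25 therefore cannot be reproduced. Everything below is in SD units.

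**Inputs from the documents.** Up to 25 patients (3.1); significance at 0.05, with two-sided tests in the earlier work (7.2). Two rates fix the group split: 50% failing (the hypothesis in 1.4) and 20% tolerant (the historical CNI rate, 3.1 Outcome Measures). Of 25 these give about 12 v 13, and 5 v 20. Because 25 is a ceiling, 20 is shown as well: 10 v 10, and 4 v 16.

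**Assumptions.** 80% power, one marker, one unadjusted t-test, equal SDs.

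**Detectable difference.** Find d such that a noncentral t with n1 + n2 − 2 degrees of freedom and noncentrality d / √(1/n1 + 1/n2) exceeds the two-sided 5% critical value with probability 0.80. The required noncentrality is 2.926 with 23 degrees of freedom and 2.963 with 18, so d is that value times √(1/n1 + 1/n2).

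| Split | √(1/n1 + 1/n2) | Detectable d | Power at 1.0 SD | Missed |
|---|---|---|---|---|
| 12 v 13 | 0.400 | 1.17 | 67% | 33% |
| 5 v 20 | 0.500 | 1.46 | 48% | 52% |
| 10 v 10 | 0.447 | 1.32 | 56% | 44% |
| 4 v 16 | 0.559 | 1.66 | 40% | 60% |

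The unit is the between-patient SD for a level, or the SD of change for a change.

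**The 20-patient statement.** It concerns changes. Section 1.2 describes a "recently published CNI to SRL conversion trial demonstrating increased percentages of PBMC/bone marrow Tregs and PBMC DCregs", which is a before-and-after design, and 7.2 describes paired analysis. A paired t-test in 20 patients detects 0.66 SD of the within-patient differences at 80% power. That is a different unit from the table, so the two cannot be set against each other directly. The point is that evidence for one contrast does not carry over to the other.

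**Signature accuracy.** This is an illustration, because the panel size for this trial is not stated. Simulate 20 pure-noise markers, keep the best 5 by absolute t, add them as signed z-scores with equal weights, and score the same patients. Correlation between markers is 0, 0.5 or 0.8 in blocks of five.

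| Split | Mean same-sample AUROC (r = 0 / 0.5 / 0.8) | Mean cross-validated AUROC, selection inside folds |
|---|---|---|
| 12 v 13 | 0.86 / 0.81 / 0.75 | 0.493 / 0.503 / 0.504 |
| 5 v 20 | 0.91 / 0.87 / 0.80 | 0.494 / 0.493 / 0.485 |

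The truth is 0.50 throughout. The q-values in 7.2 deal with multiplicity across markers. They do not remove this optimism from AUROC, sensitivity or specificity.

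**The case against.** The own-control phrase is offered as a reason for having no comparator arm. A reader might infer that it directs a paired test of success against failure. The documents do not support that: 3.1 already speaks of two groups, 4.3 plans to compare rejecting patients with successful ones, and no section prescribes a paired test for that contrast. The wording is wrong, but no wrong test follows from it.

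A reader might also infer that 7.2 commits this trial to unvalidated same-sample accuracy. Those sentences report earlier work, and the documents do not show whether that work was cross-validated. What can be said is that nothing is specified for this trial. Section 1.1 does make later use of the signatures conditional on validation, but that is future external work and does not protect planning figures taken from this study.

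Nor can the 20-patient precedent be called wholly paired. Section 7.1 does not say which study supplied the 20, and one earlier study in 1.2 compared different patients.

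The detectable differences are not a hard floor. For a post-baseline level, adjustment for baseline with an assumed correlation r multiplies d by √(1 − r²): 1.17 becomes 1.01 at r = 0.5 and 0.70 at r = 0.8. The documents give no r, and the adjustment does nothing for a baseline predictor. Low power is also ordinary in a pilot. That excuses the sample size, but not an inference drawn from a null result.

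Finally, the 3.1 sentence is rationale rather than a formal decision rule. As written, though, 'or' makes a missed correlation sufficient.

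**Conclusion.** The concern holds in three limited respects. The own-control statement in 7.1 is wrong for success versus failure; it and the 20-patient statement support within-patient change only. The inference in 3.1 from a missed correlation is unsupported: under the stated assumptions (80% power for the detectable differences, one marker, unadjusted two-sided t-test at 0.05) the detectable difference is 1.17 to 1.66 SD across the splits considered, and a true 1 SD difference is missed about 33% to 60% of the time. Section 7.2 specifies no internal validation for signature performance in this trial. The simulation shows the direction of the resulting bias, not its size here.

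This is a secondary aim of a pilot, and the harm is to planning of later studies. The primary endpoint and the tolerance-rate criterion are unaffected. Severity is minor to moderate, and the plan should be changed.

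**What to change.** **Section 3.1.** Add that a missed biomarker correlation at this sample size is inconclusive and is not by itself a reason to forgo a larger trial. Leave the tolerance-rate criterion as it is.

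**Section 7.2.** State, for this trial:
- Signature AUROC, accuracy, sensitivity and specificity come from an optimism-corrected bootstrap or repeated stratified cross-validation, with marker selection repeated inside each resample and with confidence intervals.
- The number of folds does not exceed the size of the smaller outcome group. If that group has fewer than 5 patients, use leave-pair-out: at 4 v 16, five stratified folds cannot each hold a success.
- Same-sample figures are labelled 'apparent'.
- Baseline predictors are analysed separately from change. One-year samples and suspected-rejection samples are not pooled without saying so.

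**Section 7.1.** Limit the own-control and 20-patient statements to within-patient change. Call success versus failure an exploratory between-patient comparison, and give the detectable range with its assumptions: 1.17 SD (12 v 13) to 1.46 SD (5 v 20) with 25 analysed, and 1.32 SD (10 v 10) to 1.66 SD (4 v 16) with 20.

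**Cost.** Wording and analysis code; no extra patients, samples or visits. Reported accuracy will be lower and imprecise. In the noise simulation, the widest 5th to 95th percentile range of the cross-validated AUROC was 0.27 to 0.75 at 12 v 13 and 0.18 to 0.81 at 5 v 20. The biomarker result alone would no longer argue against a larger trial.
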